8.2.1 Inclusion Criteria

Subjects must meet the following criteria:

[figure not shown]
1. Overweight (BMI 30 to 42 kg/m² inclusive) males age 18 to 60 inclusive
2. Waist circumference \geq 40 inches (101.6 cm)
3. Previously or concurrently diagnosed as having secondary hypogonadism.
4. Must have 2 morning testosterone assessments at Visit 1, collected before 10 AM, 2-4 days apart, and both of which must be \leq 300ng/dL.
5. LH >1.4 and <9.4 mIU/mL (at Visit 1 only)
6. HbA1c ≤ 7.5
7. Stable weight for last 3 months (+/- 10 pounds)
8. Lives or works within 10 miles of the gym that will be used for the study
9. Must be fit enough to participate in the fitness program
10. Ability to complete the study in compliance with the protocol requirements
11. Ability to understand and provide written informed consent

[figure not shown]
8.2.2 Exclusion Criteria

[figure not shown]
Subjects meeting any of the following criteria will be excluded from the study:

[figure not shown]
1. Any use of testosterone products (injectable, pelleted, transdermal or sublingual) in the 6 months prior to the study or any prior use of testosterone products for 12 months or longer at any time.
2. Use of testosterone, Clomid, 5 α -reductase inhibitors, hCG, androgen, estrogen, anabolic steroid, DHEA, or herbal hormone products during the study
3. Use of Clomid in the past year
4. Known hypersensitivity to Clomid
5. Allergy to soy, peanuts or latex
6. Chronic use of glucocorticoids (chronic use of inhaled or topical glucocorticoids is acceptable)
7. History of drug abuse or chronic narcotic use including methadone
8. A recent history of alcoholism or illegal substance or steroid abuse (<2 years) or presence of moderate alcohol use (>21 drinks per week)
9. Use of an investigational drug or product, or participation in a drug or medical device research study within 30 days prior to receiving study medication
10. A hematocrit $>54\%$

11. Presence or known history of hyperprolactinemia with or without a tumor (prolactin >20 ng/mL)
12. Current or history of prostate cancer or a suspicion of prostate disease unless ruled out by prostate biopsy, or a PSA>3.6
13. Current or history of breast cancer
14. Uncontrolled hypertension based on the Investigator's assessment at screening
15. History of bulimia nervosa or binge eating
16. Subject has (had) a lap band or undergone gastric bypass surgery
17. Subject has celiac disease or gluten intolerance
18. Subject has Type I diabetes
19. Subject has any condition which in the opinion of the investigator would interfere with the participant's ability to provide informed consent, comply with study instructions, possibly confound interpretation of study results, or endanger the participant if he took part in the study
20. Enrolled and randomized (if applicable) to enclomiphene in a previous enclomiphene study

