10. STUDY ENDPOINTS

The efficacy endpoints will be:

- Changes in Lean Body Mass (LBM), assessed using DXA
- Changes in waist circumference, comparing enclomiphene to placebo
- Changes from baseline in testosterone, comparing enclomiphene to placebo
- Values and changes in values from baseline in LH, HbA1c, FPG, high sensitivity C-reactive protein, Interleukin-6, tumor necrosis factor (TNF- α) receptor 2, and leptin compared to placebo
- Change in strength assessed from maximum chest and leg press weight achieved
- Changes in insulin resistance determined by HOMA-IR and Quantose IR™ (Metabolon Inc) compared to placebo
- Change in weight and BMI compared to placebo
- Values for dihydrotestosterone (DHT) and estradiol (E2), and the ratios of DHT:testosterone and testosterone:E2

█ [REDACTED]

[REDACTED]

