11.1.3 Serious Adverse Events (SAEs)

The Principal Investigator shall document all SAEs in a subject receiving study drug or during 30 days following the last dose and must be reported to the Repros Therapeutics Inc. Safety Monitor within 24 hours by Fax or telephone, even if the SAE does not appear to be drug-related. This report should include all available information at the time of notification. This notification should be followed with submitting a SAE Report Form provided by Repros Therapeutics Inc. All additional follow-up reports must be reported to the Repros Therapeutic Inc. monitor as soon as available.

Venous Thromboembolic Events

Venous thromboembolic events (VTE) should be reported to the sponsor as Serious Adverse Events regardless of whether the above-defined SAE requirements are met.

12. Concomitant Medications

Any prescription or over-the-counter medication taken during the study will be recorded in the appropriate section of the CRF. Subject must be on a stable dosage of approved concomitant medications at least 48 hours prior to initial drug administration. Unless medically necessary the dosage of chronic medications should not be changed. Unless medically necessary the addition of new medications should be avoided.

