12.1 Prohibited Medications

Use of any of the following medications during the study is prohibited:

- Any testosterone products other than the randomized study treatment
- Aromatase inhibitors (e.g. Anastrozole)
- Clomid
- 5 α -reductase inhibitors
- hCG
- Androgen
- Estrogen
- Anabolic steroid
- DHEA
- Herbal hormone products
- Chronic systemic steroid use (short term use is acceptable)

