6.7 DEMOGRAPHIC AND BASELINE CHARACTERISTICS

Demographic and baseline characteristics, consisting of previous testosterone therapy use, hypogonadal symptom history, disease history (diabetes, hypertension, hypercholesterolemia, depression, erectile dysfunction, hypothyroidism, and sleep apnea), age, and race will be summarized.

Demographics will be summarized for the Intent-to-Treat population. Demographic and baseline data will be listed for all subjects to supplement summary results. Results will be presented for each treatment group.

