6.8 EFFICACY ANALYSES

Efficacy analyses will be conducted using the Intent-to-Treat population, as defined in Section 4.1.

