6.8.5 Metabolic Parameters

HbA1c, FPG, Insulin, HOMA-IR, C-reactive protein, Interleukin-6, TNF- α , leptin, and Quantos IR levels will be measured at baseline and over time. Pairwise comparisons between treatment groups will be performed using t-tests and Wilcoxon rank-sum tests, as appropriate. Within each treatment group the statistical significance of the change/percentage change from baseline will be based on a paired t-test or Wilcoxon signed-rank test, as appropriate.

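### No named criterion keeps men on injected insulin out of the fasting-insulin and HOMA-IR comparisons, although their values there do not measure insulin resistance

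*Protocol*

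**What the plan says.** **Entry.** Among the exclusions in Protocol 8.2.2, the one that names diabetes is criterion 18: "Subject has Type I diabetes". Inclusion criterion 6 (8.2.1) caps HbA1c at 7.5, which limits glycaemia but says nothing about how it is treated. Criterion 19 lets the investigator exclude a man with any condition that would "possibly confound interpretation of study results"; it names neither diabetes nor insulin.

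**Medication.** Protocol 12.1 opens with "Use of any of the following medications during the study is prohibited" and lists hormonal products, aromatase inhibitors, 5α-reductase inhibitors and chronic systemic steroids. No glucose-lowering drug is on the list. On continuing treatment, Protocol section 12 says "Unless medically necessary the dosage of chronic medications should not be changed". The same section has all prescription and over-the-counter medication recorded on the CRF.

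**Diabetic men are foreseen.** SAP 6.7 summarises "disease history (diabetes, hypertension, hypercholesterolemia" among the baseline characteristics.

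**Endpoint and analysis.** Protocol section 10 lists "Changes in insulin resistance determined by HOMA-IR and Quantose IR™ (Metabolon Inc) compared to placebo". SAP 6.8.5 begins its list of analysed measures with "HbA1c, FPG, Insulin, HOMA-IR, C-reactive protein, Interleukin-6" and tests them between and within groups. SAP 6.8 states "Efficacy analyses will be conducted using the Intent-to-Treat population, as defined in Section 4.1", and SAP 4.1 defines that population as everyone randomised. Protocol 13.3 allows the last observation to be carried forward in some analyses, and imputes no change where there are no post-baseline data.

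**The concern.** HOMA-IR is built from fasting glucose and fasting insulin, and it reads as resistance only if the insulin is the man's own, secreted in response to his glucose. In a man who injects insulin that condition fails. If the assay detects the injected product, the result mixes product and own secretion. If it does not, the result shows only what he still secretes while treated. The documents do not describe the assay, but neither reading measures resistance.

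All men also start a diet of about 1500 calories a day and an exercise programme (Protocol 8.1.11). Section 12 permits a dose change that is medically necessary. A change in insulin dose could then show up as a change in HOMA-IR, and carrying the last observation forward could extend it to later visits.

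Insulin resistance belongs to the metabolic parameters named in the primary objective (Protocol section 7). With 15 men per arm, a single uninterpretable value has visible weight.

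**Working it through.** The plan states no sample-size or power figure (Protocol 13.1), so there is none to reproduce. The total of 45 agrees with 3 × 15 under 1:1:1 allocation.

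**Step 1. Can such a man reach the analysis?** Take a man with type 2 diabetes on a stable insulin dose with HbA1c 7.2. Criterion 6 admits him, criterion 18 does not apply, and 12.1 does not prohibit his insulin. Only a judgement under criterion 19 could exclude him. Once randomised he is in the ITT population, and SAP 6.8.5 uses his fasting insulin and HOMA-IR. No visible text sets them aside.

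**Step 2. How likely is at least one?** The share p of insulin users is not in the documents, so it is assumed. The chance is 1 − (1 − p)^n.

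| Assumed p | Arm of 15 | All 45 | Expected number per arm (15p) |
|---|---|---|---|
| 1% | 14% | 36% | 0.15 |
| 2% | 26% | 60% | 0.30 |
| 3% | 37% | 75% | 0.45 |
| 5% | 54% | 90% | 0.75 |
| 10% | 79% | 99% | 1.50 |

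For example, at 3%: 1 − 0.97^15 = 0.37 and 1 − 0.97^45 = 0.75.

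**Step 3. What does one affected value do to an arm's summary?** The documents give no SD for insulin or HOMA-IR, so the distortion is expressed as k SD. The arm mean moves by k/15 SD, and the expected arm SD is multiplied by √(1 + k²/15).

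| k | Shift in mean (SD) | SD multiplied by |
|---|---|---|
| 2 | 0.13 | 1.13 |
| 5 | 0.33 | 1.63 |
| 10 | 0.67 | 2.77 |

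**Step 4. What does it do to the test?** With 15 per arm and two-sided 0.05, about 80% power needs a difference of roughly 1.02 SD (normal approximation 0.798; simulated t-test 0.76). The simulation shifted one of 15 values in one arm by k SD in a random direction. It used 20,000 runs for the t-test, and 4,000 for the SAP's rule of switching to a rank test when Shapiro-Wilk rejects.

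| k | Power, t-test | Power, SAP rule | Type I error, t-test | Type I error, SAP rule |
|---|---|---|---|---|
| 0 | 0.76 | 0.76 | 0.050 | 0.052 |
| 2 | 0.72 | 0.71 | 0.050 | 0.054 |
| 5 | 0.51 | 0.65 | 0.040 | 0.041 |
| 10 | 0.32 | 0.65 | 0.012 | 0.050 |

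The damage is lost power and distorted means and SDs. The false-positive rate is not raised. That result assumes the distortion is unrelated to treatment, which the random direction represents.

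**The case against.** The case for leaving the plan alone has several sound parts.

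- **Criterion 19 may already keep these men out.** It covers conditions that could confound the results. It is a matter of opinion, though, and sites may apply it differently. It means that such a man may be eligible, not that he certainly is.
- **The rank-test fallback in SAP 6.1 limits the leverage of an extreme value.** This stands: even at 10 SD, power under that rule is 0.65, against 0.32 for the t-test. It does not make the value valid, and means and SDs are still reported.
- **On a stable dose, part of the injected contribution cancels in the change from baseline.** This also stands. It reduces the distortion but does not turn the measurement into one of resistance.
- **The study is hypothesis-generating, this is one endpoint group among many, and SAP 6.1 permits additional analyses.** This lowers the stakes. An analysis chosen after results are seen is still weaker than one sentence written beforehand.

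Two stronger readings are tempting. A reader might infer that the insulin-resistance results of whole arms are meaningless, or that a false treatment difference is likely. The documents support neither: the affected values belong to individual men who may number zero, and Step 4 shows no inflation of type I error.

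A reader might also size the effect in HOMA-IR units by supposing that a man's measured insulin drops back to his own level when his injections stop. That would hold glucose fixed while insulin is withdrawn, assume that the whole injected contribution is lost, and assume that the assay reads it. The documents give no basis for any of these. Nor should the 36-75% chance for all 45 men be paired with the shift in one arm; the matching figure is 14-37%.

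**Conclusion.** The gap is real and narrow. Following the visible text, fasting insulin and HOMA-IR from any insulin-treated man who is randomised enter a listed endpoint although they do not measure resistance. At an assumed 1-3% share, the chance that a given arm of 15 contains at least one such man is 14-37%, and that the trial does is 36-75%. One value wrong by 5 SD would move the arm mean by 0.33 SD and lower power at a 1.02 SD difference from 0.76 to 0.51 with the t-test, or to 0.65 under the SAP's fallback.

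These figures rest on the assumed share and on a distortion expressed in SD units. Parts of both documents are redacted or removed and could hold a handling rule; the visible exclusion list, medication list and analysis sections contain none. The point does not touch the other endpoints or the conduct of the trial as a whole.

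**What to change.** Before unblinding, which here means before the first unblinded interim analysis, add to SAP 6.8.5:

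- Fasting insulin and HOMA-IR from men using exogenous insulin at baseline, identified from the concomitant-medication CRF, are listed but left out of the insulin and HOMA-IR comparisons.
- Those values are not refilled by carrying the last observation forward or by imputing no change (Protocol 13.3).
- The number of such men is reported per arm, and they stay in every other endpoint.
- Insulin started or changed after randomisation is handled in a sensitivity analysis, not by exclusion from the main comparison. Treatment may affect those events, and removing men because of them would select on outcome.

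Quantose IR stays as planned, because the documents do not say what goes into it and so give no ground for setting it aside. Criterion 18 need not change for this purpose; narrowing the population is a separate trade-off.

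The cost is a short SAP addition using data already collected, provided that the medication record shows start dates. The downside is slightly fewer men in the insulin and HOMA-IR analyses: an expected 15 × 0.01 = 0.15 to 15 × 0.03 = 0.45 per arm at the assumed 1-3%.

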10. STUDY ENDPOINTS

The efficacy endpoints will be:

- Changes in Lean Body Mass (LBM), assessed using DXA
- Changes in waist circumference, comparing enclomiphene to placebo
- Changes from baseline in testosterone, comparing enclomiphene to placebo
- Values and changes in values from baseline in LH, HbA1c, FPG, high sensitivity C-reactive protein, Interleukin-6, tumor necrosis factor (TNF- α) receptor 2, and leptin compared to placebo
- Change in strength assessed from maximum chest and leg press weight achieved
- Changes in insulin resistance determined by HOMA-IR and Quantose IR™ (Metabolon Inc) compared to placebo
- Change in weight and BMI compared to placebo
- Values for dihydrotestosterone (DHT) and estradiol (E2), and the ratios of DHT:testosterone and testosterone:E2

█ [REDACTED]

[REDACTED]

11. ASSESSMENT OF SAFETY

11.1 Adverse Events

11.1.1 Reporting Adverse Experiences

Any AE (clinical sign, symptom, or disease) temporally associated with the use of this investigational drug, whether or not considered related to the investigational product, shall be documented on the CRF. All AEs reported by the subject or observed by the Principal Investigator will be individually listed. The signs and symptoms, time of onset (24-hour clock), duration, action taken and follow-up procedures will be reported.

11.1.2 Definitions

Adverse Event – Any untoward medical occurrence in a clinical investigation subject administered a drug and does not necessarily have a causal relationship with this treatment. An AE can therefore, be any unfavorable and unintended sign (including an abnormal laboratory finding if the investigator considers this finding to be an adverse event), symptom, or disease temporally associated with the use of an investigational product, whether or not related to the investigational product.

Serious Adverse Event (SAE) – An adverse drug experience that results in any of the following outcomes: death, a life-threatening experience, requires or prolongs subject hospitalization, results in persistent or significant disability/incapacity, or is a congenital anomaly or birth defect.

Venous thromboembolic events (VTE) should also be reported to the sponsor as Serious Adverse Events regardless of whether the above-defined SAE requirements are met.

Unexpected Adverse Event: Any adverse event that is not identified in nature, severity, or frequency in the current Investigator's Brochure.

Additionally, the Principal Investigator will evaluate all AEs as follows:

Action taken: whether or not the AE caused the subject/patient to discontinue the study medication.

Intensity, to be graded as:

DEGREE	DESCRIPTION
Mild	Awareness of signs and symptoms; easily tolerated
Moderate	Discomfort sufficient to interfere, but not prevent daily activity
Severe	Unable to carry out usual activity

Relationship to study medication, to be graded as:

DEGREE	DESCRIPTION
Definitely	There is evidence of exposure to the study drug, for example, reliable history or acceptable compliance assessment; the temporal sequence of the AE onset relative to the medication is reasonable; the AE is most likely to be explained by the treatment than by another cause; the AE shows a pattern consistent with previous knowledge of the treatment.
Probably	There is evidence of exposure to the study drug; the temporal sequence of the AE onset relative to medication administration is reasonable; the AE is more likely explained by the treatment than by another cause.
Possibly	There is evidence of exposure to the study drug; the temporal sequence of the AE relative to the medication administration is reasonable; the AE could have been due to another equally likely cause.
Probably not	There is evidence of exposure to the study drug; there is another more likely cause of the AE.
Definitely not	The subject/patient did not receive the study drug; or temporal sequence of the AE onset relative to administration of the study drug is not reasonable; or there is another obvious cause of the AE.

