8.2 Selection and Withdrawal of Subjects

Subjects will be selected during screening based on the inclusion and exclusion criteria and clinical assessments listed below. Subjects will be discontinued from the study prematurely if:

- Unacceptable adverse events considered by the investigator to be associated with use of the study drug occur
- Hematocrit >54% and confirmed upon repeat
- The subject requests to be withdrawn from the study
- A need for concomitant medication prohibited by the protocol arises

- The Principal Investigator decides that it is in the subject's best interest
- The subject is noncompliant with the protocol at Sponsor/Investigator discretion

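### Apart from VTE, the SAE definition is a closed list of five outcomes, so a confirmed-hematocrit withdrawal or an outpatient cancer diagnosis need not be reported within 24 hours or counted as serious

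*Protocol*

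**What the plan says.** Protocol 11.1.2 defines an SAE by outcome: "An adverse drug experience that results in any of the following outcomes: death, a life-threatening experience, requires or prolongs subject hospitalization", followed by lasting disability or incapacity and by congenital anomaly or birth defect. The next sentence makes one addition: "Venous thromboembolic events (VTE) should also be reported to the sponsor as Serious Adverse Events regardless of whether the above-defined SAE requirements are met". Section 11.1.3 repeats it.

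Section 11.1.3 gives sites 24 hours to tell the sponsor's Safety Monitor of an SAE, "even if the SAE does not appear to be drug-related". Section 11.1.1 sends other adverse events to the CRF and states no deadline.

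The conditions that matter here appear elsewhere in the protocol:

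- Section 8.2 ends a subject's participation for "Hematocrit >54% and confirmed upon repeat". A hematocrit above the same limit also bars entry (8.2.2, criterion 10).
- Section 8.2.2 excludes "Current or history of prostate cancer or a suspicion of prostate disease unless ruled out by prostate biopsy" (criterion 12, which also sets a PSA limit) and "Current or history of breast cancer" (criterion 13).

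SAP 6.9.1 has the same content in the May 2016 issue and in the July 2016 amendment. It plans separate summaries of serious TEAEs and of TEAEs leading to withdrawal, and a listing of all AE data.

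**The concern.** A purely outcome-based definition misses events that are grave but have not yet caused death, admission or disability. The VTE sentence shows that the authors met this problem: it is needed only because an important event can miss every listed outcome. It was solved for one event type.

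Seriousness does two jobs in this trial. It decides whether the Safety Monitor hears of an event within a day, and it decides which events enter the SAP's serious-TEAE summary. Protocol 13.2.1 allows the study to be stopped for safety at any time, and the SAE report is the only route in the visible text that carries a deadline. A site that applied 11.1.2 exactly could remove a man for a safety laboratory limit, or record a new cancer, without either job being done.

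**Working it through.** The plan states no figure on this point, so this is a check of the text.

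**Inputs**

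1. Listed outcomes (11.1.2): "death, a life-threatening experience, requires or prolongs subject hospitalization, results in persistent or significant disability/incapacity, or is a congenital anomaly or birth defect". That is five.
2. Named exceptions (11.1.2, 11.1.3): VTE. That is one.
3. Criteria in 11.1.1 to 11.1.3 that rest on medical importance or on judgement of jeopardy: none.
4. Reporting clock: 24 hours for SAEs (11.1.3); none stated for other AEs (11.1.1).
5. Laboratory findings: an AE only if the investigator regards them as one (11.1.2).

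Count: 5 + 1 = 6 routes to SAE status, of which 0 rest on medical importance.

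**Three cases run through the rules**

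| Step | VTE treated without admission | Confirmed hematocrit >54%, no symptoms | Prostate or breast cancer found as an outpatient |
|---|---|---|---|
| Is it an AE? | Yes | Only if the investigator says so | Yes, it is a disease |
| Does it meet a listed outcome? | Not necessarily | No | Only if judged life-threatening or disabling, or if admission follows |
| Is it a named exception? | Yes | No | No |
| Is a 24-hour report assured? | Yes | No | No |
| Is a place in the serious-TEAE summary assured? | Yes, if treatment-emergent | No | No |
| Where else does it show? | All TEAE tables | Disposition count; TEAE and withdrawal tables if recorded as an AE | TEAE tables and AE listing |

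**Hematocrit.** Section 8.2 lists the hematocrit limit as a reason for discontinuation separate from unacceptable adverse events. A site can therefore withdraw the man under the hematocrit rule and record no AE. He is then absent from the TEAEs leading to withdrawal, and the visible text of SAP 6.5 only counts completers and early discontinuations.

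**Cancer.** The intensity scale in 11.1.2 grades tolerability and effect on daily activity. A symptom-free cancer can be graded mild, so the maximum-severity summary in SAP 6.9.1 does not make up for a missing serious flag.

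**Opening words.** The SAE definition begins with an adverse drug experience, which suggests that the drug is involved. The AE definition in the same section and the reporting rule in 11.1.3 are neutral on relatedness.

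**The case against.** The strongest reply is that the gap is narrow and other provisions cover much of it. Several parts of that reply stand.

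- **Judgement on cancer.** A reader might infer that an outpatient cancer is always non-serious under 11.1.2. The text does not say so. The life-threatening outcome is not defined further, an investigator may apply it to a cancer, and a later admission would also qualify. The point is that the classification is left to varying judgement.
- **Status of the cancers.** Prostate and breast cancer appear in the visible text only as entry exclusions, without a rationale, in a list that also bars latex allergy and celiac disease. That they are recognized on-study risks is an inference. Hematocrit has direct support, since it governs both entry and discontinuation.
- **Other routes.** Subjects are called every two weeks and asked about adverse events (8.1.1, 8.1.11), and the sponsor monitors records (14.3, 14.5). A reader might infer that the sponsor learns of such an event only at an interim analysis, months later. The documents do not show that, and an interim look compares arms whereas an SAE report concerns one subject.
- **Loss of signal.** A reader might note that reclassifying one event moves an arm from 1/15 = 6.7% to 0/15. That only restates the reclassification. An event recorded as an AE remains in the TEAE tables and listings.
- **Drug-experience wording.** Section 11.1.3 already settles that unrelated SAEs are reported, so this is untidy drafting with no practical effect on a site that reads both sections.
- **Arterial events.** One might wish to add them to the named exceptions. No visible passage names an arterial risk, so the documents give no basis for it.
- **Unseen material.** The SAE Report Form, the Study Procedures Manual and the study-procedures section are not visible and may add criteria; 6.3 also binds the trial to FDA regulations and GCP. Sections 11.1.1 to 11.1.3 nevertheless read as complete.

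None of this supplies a medical-importance criterion or a deadline for the two cases.

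**Conclusion.** The point holds in a limited form. Followed exactly, 11.1.2 and 11.1.3 do not assure a 24-hour report or a place in the serious-TEAE summary for a confirmed-hematocrit discontinuation, or for an outpatient cancer that the investigator does not judge life-threatening. Hematocrit is the firmer example, because the protocol itself removes the subject and the event may not even be recorded as an AE.

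The gap concerns classification and speed of reporting. It does not affect the efficacy analyses, and it does not show that events would vanish from the study report. The documents give no expected frequency for these events, so no rate or length of delay can be attached. The conclusion assumes that no unseen form or manual adds a seriousness criterion. It should be corrected, since the change is small and bears on subject safety.

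**What to change.** Amend the protocol as follows:

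1. In 11.1.2, add a sixth limb: *or is an important medical event that, in the investigator's judgement, may jeopardize the subject or require intervention to prevent one of the outcomes listed above*.
2. In 11.1.2 and 11.1.3, extend the VTE sentence to any subject discontinued under the protocol's own confirmed-hematocrit rule in 8.2, and to newly diagnosed prostate or breast cancer. Naming these events matters because the sixth limb alone would still leave them to judgement. It also captures a hematocrit withdrawal that no one recorded as an AE.
3. In 11.1.2, replace the drug-experience opening with *any adverse event, whether or not considered related to study drug*, to agree with 11.1.3.

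The SAP needs no new table, because its serious-TEAE summary follows the classification. The hematocrit limit, the discontinuation rules and treatment are unchanged; only reporting changes. The cost is a few sentences in an amendment, a memo to sites, a few more 24-hour reports and a slightly higher SAE count.
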